6.1 Assessment and Reporting of Adverse Events

6.1.1 Investigator's Responsibilities

Throughout the course of the study, all efforts will be made by the Investigators to remain alert to possible AEs. The first concern will be the safety and welfare of the subject and for providing appropriate medical intervention, as indicated. Detailed information regarding adverse events (AEs) will be recorded by the Investigator at the time an adverse event occurs using an *Adverse Event Questionnaire*, provided as part of the CRFs for the study. All adverse events will be recorded from the day of enrollment (Day 0) to termination of study, approval of the PMA, or when the subject exits the study, whichever is the last, even if the event was acknowledged as a risk factor in the *Informed Consent Form*.

AEs will be recorded on an *Adverse Event Questionnaire* and will include the following information:

- Date of onset
- Date reported to the clinic
- Description of the AE
- Seriousness
- Investigator's assessment of the relationship of the AE to the device and/or procedure
- Treatment
- Outcome

6.1.1.1 Unanticipated Adverse Device Effects

Unanticipated adverse device effects (UADEs) must be reported directly to the clinical center's reviewing IRB and the Sponsor, Cochlear Americas, within 10 working days of knowledge of the event, or as dictated by the specific IRB policy, whichever is sooner. Information regarding the UADE will be recorded on the *Unanticipated Adverse Device Effect Report*, provided with the CRFs for the study.

6.1.1.2 Adverse Event Follow-up

All AEs must be followed until resolution, or the condition stabilizes. The Investigator is responsible to ensure that follow-up includes any supplemental investigations as may be indicated to elucidate as completely as possible the nature and/or causality of the AE. This may include additional laboratory tests or investigations, or consultation with other health care professionals. Cochlear or its designee may request that the Investigator perform or arrange for the conduct of supplemental measurements and/or evaluations. AE follow up information will be recorded using a *Follow Up to a Previously Reported Adverse Event Questionnaire*, provided with the CRFs for the study.

6.1.2 Sponsor's Responsibilities

All AEs will be reported annually to FDA in accordance with the IDE regulation [FDA 21 CFR Part 812.150(b)(5)]. All unanticipated adverse device effects (UADEs) will be reported

to FDA within 10 calendar days of the event in accordance with FDA 21 CFR Part 812.46(b) and 812.150(b)(1).

Cochlear Americas or its designee will notify all participating Investigators of any new information that alters the current risk-benefit assessment of the study device or that would be sufficient to consider changes in management of the Nucleus cochlear implant or in the overall conduct of the trial.

6.2 Protocol Deviations

A protocol deviation refers to a study-related activity that is not in compliance with the investigational protocol. Deviations that are required to protect the life or well-being of a subject do not require prior approval from the Sponsor and should be implemented immediately. The IRB and Sponsor must be notified within 5 (five) days of the event.

If a subject is unable to return for follow-up before the closure of a study visit window (+/-30 days for postactivation study visits), or if protocol defined assessments or parts thereof are omitted or completed incorrectly, the event is to be noted on the Protocol Deviation Log provided to the Investigator in the study Regulatory Binder. Depending on the type or severity of the deviation the Investigator may be required to notify the IRB and/or Sponsor if the deviation impacts safety or performance of the subject or data integrity.

7.0 Study Completion

7.1 Completed Subjects

Each subject in the study will be considered completed when all assessments through 12 months postactivation have been performed in accordance with the study protocol. To be considered a primary endpoint success, subjects must retain their originally implanted device.

7.2 Evaluation PRIOR to Re-implantation with a Long Electrode

Some individuals may to have the Nucleus Hybrid S-RW cochlear implant removed and replaced with a standard, long electrode array cochlear implant. This has typically been in cases where individuals have experienced a profound or complete loss of residual hearing (6 of the 50 subjects implanted as of November 8, 2013 as documented in the Nucleus Hybrid L24 pivotal trial (P130016).

In order to ensure that accurate information is gathered for any subject electing to undergo explantation and re-implantation with a long array, additional data will be collected prior to re-implantation. This evaluation will include the following information and will follow the procedures described in the annual evaluation schedule:

- Audiometric testing
- Speech perception testing
- Psychophysical and electrical impedance measurements
- Otologic/medical guestionnaire

7.3 Evaluation FOLLOWING Re-implantation with a Long Electrode

Subjects who elect to be implanted with a standard cochlear implant in the test ear in place of the Nucleus Hybrid S-RW cochlear implant will be required to complete the study protocol as outline above. That is, they will be asked to follow the same postoperative schedule and procedures up to their 12 Month post-activation interval.

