2.0 Study Objective

To evaluate the feasibility of implanting the Cochlear[™] Nucleus[®] Hybrid S-RW in newly implanted adults with expanded indications for candidacy, using performance on an open set monosyllabic word recognition measure at the 12 month postactivation visit as primary efficacy endpoint.

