2.3 Study Procedures

Subjects will be assessed for study purposes preoperatively as well as at intervals corresponding to the initial activation of the device, 3 months postactivation, 6 months postactivation, and 12 month postactivation. Preoperatively, candidates will be

assessed in the unaided and aided (i.e., with appropriately fit hearing aids) conditions to determine their candidacy for inclusion into the study. Once determined a candidate, a preoperative baseline evaluation will be conducted to establish baseline measures. Postoperatively, Best Unilateral (e.g., Hybrid or Electric Alone) and Best Bilateral (e.g., Combined or Bimodal) conditions will be tested to evaluate performance with the Hybrid implant. The test interval for the primary endpoint of the study for device safety and efficacy is the 12-month postactivation evaluation. Non-study follow-up evaluations may also take place at the discretion of the study site as part of routine care.

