8.3 Efficacy Measurements

As appropriate under a feasibility study protocol, the goal is to establish preliminary effectiveness data to facilitate the development of a pivotal study. As such, no formal statistical hypotheses will be tested. At a minimum, individual data will be tabulated and summarized for all measures to establish the proportions of those subjects showing improvement, no change, and decrement in performance.

8.3.1 The efficacy objectives include:

- 1. To understand if measurable low frequency thresholds can be maintained with implantation through the round window using the Hybrid S-RW
- 2. To understand if implantation through the round window with the Hybrid S-RW results in improved postoperative speech perception outcomes in both quiet and noise for patients with measurable postoperative low frequency thresholds
- 3. To understand if implantation through the round window with the Hybrid S-RW results in improved postoperative speech perception outcomes in both quiet and noise for patients without measurable postoperative low frequency thresholds

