9.0 Missing Data

All efforts will be put forth to ensure near complete follow-up, with particular focus on the assessment of the primary outcome and occurrence of adverse events. Regular

reminders of subject follow-up due dates will be provided to participating centers to facilitate scheduling of follow-up visits.

In the event a subject is withdrawn prior to the 12month assessment, the primary analysis of the primary efficacy endpoint will involve imputing the pre-operative CNC word test score for the 12 month CNC word test. This is equivalent to treating each subject with a missing 12 month result as unchanged from baseline.

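### A subject re-implanted with a long electrode before 12 months is no success under Section 7.1, yet Sections 7.3 and 8.3 let the long-electrode score count as improvement

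*Protocol*

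**What the plan says.** Five parts of the protocol bear on a subject whose S-RW is exchanged for a standard long electrode before the 12-month visit.

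- **Section 2.0** defines the endpoint, "using performance on an open set monosyllabic word recognition measure at the 12 month postactivation visit as primary efficacy endpoint", under an objective that names the S-RW. Section 2.3 adds that the postoperative "conditions will be tested to evaluate performance with the Hybrid implant".
- **Section 7.1** says: "To be considered a primary endpoint success, subjects must retain their originally implanted device". Its condition for completing the study is separate and does not require the device to be retained.
- **Section 7.3** keeps the re-implanted subject under test: "they will be asked to follow the same postoperative schedule and procedures up to their 12 Month post-activation interval".
- **Section 8.3** promises, as a minimum, individual tabulations and the "proportions of those subjects showing improvement, no change, and decrement in performance". Objective 3 in Section 8.3.1 asks whether round-window implantation "with the Hybrid S-RW results in improved postoperative speech perception outcomes in both quiet and noise for patients without measurable postoperative low frequency thresholds".
- **Section 9.0** opens its imputation rule with "In the event a subject is withdrawn prior to the 12month assessment" and carries the preoperative CNC score forward. It adds: "This is equivalent to treating each subject with a missing 12 month result as unchanged from baseline".

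Section 7.2 foresees replacement, says it has typically followed profound or complete loss of residual hearing, and cites 6 of 50 subjects in the L24 pivotal trial. It requires speech perception testing before explantation but gives that score no role in the 12-month result.

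**The concern.** Section 7.1 plainly means that a subject who loses the S-RW should not count in its favour. But it acts through the word success, and no summary in the protocol is built on success. The classes in Section 8.3 depend on the direction of change in score and carry no device condition. Section 7.3 then supplies a score from a different device at what may be the primary visit.

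Followed literally, the plan can therefore report a long-electrode result as improvement with the S-RW. The summaries affected are those meant to inform a pivotal study. Objective 3 is the most exposed, because replacement typically follows loss of residual hearing and such a subject is likely to fall in the group without measurable low-frequency thresholds.

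**Working it through.** The protocol gives no sample size calculation or test, so there is no figure of its own to reproduce. The check has four steps.

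**1. Which clock?** Section 7.3 does not say. Its reference to the same postoperative schedule could suggest a restart. Section 2.4 expects 15 to 18 months of participation in all. Allow up to 90 days (about 3 months) before surgery (Section 5.4), about 1 month to activation (4 weeks, Section 5.6.2.1) and 12 months of follow-up: 3 + 1 + 12 = 16 months, inside that range. If replacement surgery takes place m months after first activation and the clock restarts, the total is 3 + 1 + m + 1 + 12 = 17 + m, which passes 18 once m exceeds 1. With no preoperative time at all it is 14 + m, which passes 18 once m exceeds 4. The original clock fits better, but the text does not settle the question.

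**2. What happens on the original clock?**
- The subject attends the 12-month visit with the long electrode. If hearing is un-aidable, the notes to Section 5.6.2.2 make CI alone the best unilateral condition, so the long-electrode score becomes the implanted-ear score.
- Section 7.1: not a success.
- Section 8.3: improved, unchanged or worse according to that score.
- Section 9.0: not triggered, because the subject is neither withdrawn nor missing a result. Section 7.4 does not list re-implantation as a reason for discontinuation, though it has an open category for other reasons.

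**3. Size per case.**
- *Proportions.* With n = 10 (Section 4.0 allows up to 10), one subject is 1/10 = 10 points. For illustration, assume 7 of 9 retainers improve and one subject is re-implanted and scores higher with the long electrode. The improved proportion is 8/10 if that score counts, 7/10 if it does not, and 7/9 = 78% if the subject is left out.
- *Mean.* Section 4.1 limits the entry score in the implanted ear to 20% to 60%. Compared with counting the subject as unchanged, one long-electrode score moves a mean of 10 by at most (100 − 20)/10 = +8 points and at least (0 − 60)/10 = −6 points. These are bounds, not estimates, and the sign is open.

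**4. How likely is a case?** I read the 6/50 in Section 7.2 as the number replaced: p = 0.12, exact (Clopper-Pearson) 95% interval 4.5% to 24.3%. Applying it to 10 subjects over 12 months is an assumption, since the device differs and no follow-up time is given.

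| Rate | Expected in 10 | P(at least 1) = 1 − (1 − p)^10 | P(at least 2) |
|---|---|---|---|
| 12% | 1.2 | 1 − 0.88^10 = 72% | 34% |
| 4.5% (lower limit) | 0.45 | 37% | 7% |
| 24.3% (upper limit) | 2.4 | 94% | 74% |
| 6% (half the cited rate) | 0.6 | 1 − 0.94^10 = 46% | 12% |

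**The case against.** The strongest reply is that Section 7.1 already bars the damaging reading. It can only be aimed at the re-implantation described in the two sections after it. Section 7.3 is a follow-up rule, not an analysis rule, and Section 8.3 describes a minimum tabulation. A subject can have a higher score without being a success, so the statements need not contradict each other. Denominators and separate tables are ordinary SAP content. No hypothesis is tested, and individual data and adverse event listings would show the replacement.

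Much of this stands. The intent is clear from Sections 2.0, 2.3 and 7.1, and the consequence is small. It does not remove the gap: the protocol itself fixes a success condition, a follow-up rule and a classification, and the condition is not attached to the classification.

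Three stronger readings are tempting but not supported.
- *The two sentences of Section 9.0 name different sets of subjects.* The second begins by calling itself equivalent to the first. It explains that rule and does not set a rival one.
- *The wording would bias results in favour of the S-RW.* It could, but a subject re-implanted shortly before the visit would be tested with little experience of the new device, and the bounds of +8 and −6 allow either direction.
- *The protocol must prescribe how a group mean handles these subjects.* Section 8.1 speaks only of group effects and Section 8.3 names no mean. That choice belongs to the SAP.

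**Conclusion.** The point holds and is minor. Sections 7.1, 7.3 and 8.3 need to be reconciled, because a long-electrode CNC score can be reported as improvement with the S-RW at the primary visit. This conclusion rests on the original clock, which is the better-supported reading but is not stated.

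The effect is up to 10 points on a Section 8.3 proportion per case with 10 subjects, and more per case if fewer are implanted. The direction of any effect on a mean is uncertain. At least one case is more likely than not if the L24 figure carries over, and close to even at half that rate; both rest on an assumed rate. No error rate or power is affected, and the harm is confined to descriptive summaries.

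**What to change.** 1. In Section 8.3, state that a subject whose S-RW is replaced before 12 months stays in the denominator, is shown in a separate row as S-RW replaced, and is not counted as improved, in line with Section 7.1.
2. Tabulate long-electrode scores separately, outside the S-RW 12-month summaries and outside objective 3. List the pre-explant S-RW score collected under Section 7.2 with its time point.
3. In Section 7.3, state which activation starts the 12-month interval.

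The cost is a few sentences and one table row, with no new visit. The improved proportion may be lower than under the current wording. The decision to re-implant is not affected. The wording is best settled before any 12-month scores are seen.

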7.4 Discontinued Subjects

Any subject may voluntarily discontinue the study at any time without prejudice. The Investigator may discontinue a subject from the study at any time if (s)he considers that remaining in the study compromises the subject's health or the subject is not sufficiently cooperative. In either event, reason(s) for discontinuation should be recorded on a study withdrawal form, provided as part of the CRFs for the study.

Possible reasons for study discontinuation include the following:

- AE necessitating discontinuation from the study.
- The subject is lost to follow-up.
- Voluntary decision to withdraw consent made by the subject⁹.
- Investigator decision¹⁰.
- Other reason.

In case of a subject lost-to-follow-up, the Investigator must attempt to contact the subject (or relative/family contact) by phone, email or letter at least three times. If attempts are unsuccessful, the 'subject withdrawal' form is to be completed in the study file and reported, as appropriate, in required reports to the Sponsor, IRB and FDA.

7.5 Premature Study Termination

The Sponsor reserves the right to discontinue the study for any safety, ethical or administrative reason at any time. Subjects already implanted with the device being

⁹ Withdrawal of consent is defined as the subject's voluntary decision to revoke consent to continue participation in the study.

¹⁰ Subject withdrawal from the study is defined as an Investigator decision. The Investigator may elect to withdraw a subject from the study at any time if he/she considers that remaining in the study compromises the patient's health or if the Investigator considers the subject lost to follow-up.

studied will continue to be supported, independent of any decision made about study continuation.

8.0 **Data Analyses**

8.1 Sample Size

Since this protocol describes a feasibility study in a limited number of subjects, sample size estimates were not made. Individual outcomes will be compared, along with group effects, across pre- and postoperative test conditions for both audiometric and speech perception outcomes.

8.2 Safety Measurements

No formal statistical hypothesis will be tested. The number and percent of patients with adverse events will be reported and tabulated; as well as compared to the commercially available Hybrid L24 system. Adverse events will be summarized by event type, severity, seriousness, as well as relatedness to the device and implant procedure. Since the proposed study involves a limited number of subjects, group analyses are not planned.

8.3 Efficacy Measurements

As appropriate under a feasibility study protocol, the goal is to establish preliminary effectiveness data to facilitate the development of a pivotal study. As such, no formal statistical hypotheses will be tested. At a minimum, individual data will be tabulated and summarized for all measures to establish the proportions of those subjects showing improvement, no change, and decrement in performance.

8.3.1 The efficacy objectives include:

- 1. To understand if measurable low frequency thresholds can be maintained with implantation through the round window using the Hybrid S-RW
- 2. To understand if implantation through the round window with the Hybrid S-RW results in improved postoperative speech perception outcomes in both quiet and noise for patients with measurable postoperative low frequency thresholds
- 3. To understand if implantation through the round window with the Hybrid S-RW results in improved postoperative speech perception outcomes in both quiet and noise for patients without measurable postoperative low frequency thresholds

9.0 Missing Data

All efforts will be put forth to ensure near complete follow-up, with particular focus on the assessment of the primary outcome and occurrence of adverse events. Regular

reminders of subject follow-up due dates will be provided to participating centers to facilitate scheduling of follow-up visits.

In the event a subject is withdrawn prior to the 12month assessment, the primary analysis of the primary efficacy endpoint will involve imputing the pre-operative CNC word test score for the 12 month CNC word test. This is equivalent to treating each subject with a missing 12 month result as unchanged from baseline.

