5.6.3.3 Speech Perception Testing

- S₀N₀ AzBio Sentences in Noise One list at 60 dB(A) with a +5 dB SNR lpsilateral Listening Conditions:
 - Electric alone (both ears plugged)
 - If applicable, Acoustic Alone (contralateral ear plugged)
 - If applicable, Hybrid (contralateral ear plugged)

Bilateral Listening Conditions:

- Bimodal (ipsilateral ear plugged)
- If applicable, Combined
- CNC Word Test (Quiet) Two lists at 60 dB(A)

Ipsilateral Listening Conditions:

- Electric alone (both ears plugged)
- If applicable, Acoustic Alone (contralateral ear plugged)
- If applicable, Hybrid (contralateral ear plugged)

Bilateral Listening Conditions:

⁸ Bone conduction measures at 125 Hz are optional based on potential audiometric equipment limitations.

- Bimodal (ipsilateral ear plugged)
- If applicable, Combined

Note: If the subject lost acoustic hearing in the implanted ear and does not utilize the acoustic component, the best unilateral condition is the same as electric alone and therefore does not need to be evaluated.

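### Baseline imputation counts every withdrawn subject as unchanged, so the 12-month CNC decrement proportion can be understated but never overstated

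*Protocol*

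**What the plan says.** Section 9.0 sets the rule. It applies "In the event a subject is withdrawn prior to the 12month assessment", with no distinction by reason, and states that "the primary analysis of the primary efficacy endpoint will involve imputing the pre-operative CNC word test score for the 12 month CNC word test". It then spells out the consequence: "This is equivalent to treating each subject with a missing 12 month result as unchanged from baseline".

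Section 8.3 plans no hypothesis test. The minimum summary, for all measures, is a tabulation of individual data "to establish the proportions of those subjects showing improvement, no change, and decrement in performance". It says that the results are meant to help design a pivotal study.

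Three other sections matter here:

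- Section 5.6.3.3 and the visit table in section 5.7 schedule CNC testing at 3, 6 and 12 months after activation, so a withdrawn subject may already have one or two post-activation scores.
- Section 7.4 lists among the reasons for leaving "AE necessitating discontinuation from the study".
- Section 7.3 says that subjects re-implanted with a long electrode "will be required to complete the study protocol as outline above". Those who stay are therefore tested to 12 months and fall outside the imputation rule.

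**The concern.** Setting a missing result to baseline is usually defended as conservative, and for improvement it is: a withdrawn subject can never be counted as improved. The summary here has three categories, though, and the same rule also prevents a withdrawn subject from being counted as worse. For the decrement category it is therefore favourable to the device.

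This would matter little if withdrawal had nothing to do with outcome, but the protocol gives reasons to think it might. An adverse event is a listed reason for leaving. Section 10.0 names permanent loss of residual hearing as a risk and says its impact will be judged in light of speech perception, so the decrement proportion bears on risk as well as benefit. Section 4.1 requires an aided score of 20% to 60% in the ear to be implanted, so there is room to fall. A subject whose score had dropped at 3 or 6 months and who then withdrew would appear in the primary table as unchanged. With at most 10 subjects, one such case is visible in the headline proportion that is carried into the pivotal design.

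**Working it through.** The protocol gives no withdrawal rate, decrement rate or sample-size calculation, so there is no planned figure to reproduce. What can be checked is the direction and possible size of the effect.

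**Inputs.** N = 10, the maximum in the synopsis and section 4.0. Imputed change = pre-operative score − pre-operative score = 0, by section 9.0. The numbers of withdrawals and decrements below are assumptions.

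**Direction.** Let D_obs be decrements among completers, w the number withdrawn, and D_miss the number of withdrawn subjects who in truth declined (0 ≤ D_miss ≤ w).

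- Plan: D_obs / N
- Full data: (D_obs + D_miss) / N
- Bias of the plan: −D_miss / N

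The bias is never positive. This does not depend on the threshold used to define a decrement or on the withdrawal rate. The plan's figure also never exceeds the completers-only figure D_obs / (N − w), because the numerator is the same and the denominator is at least as large.

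**Size, with one decrement among completers (assumed).**

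| Withdrawn | Plan | Completers only | All withdrawn declined |
|---|---|---|---|
| 1 | 1/10 = 10% | 1/9 = 11.1% | 2/10 = 20% |
| 2 | 1/10 = 10% | 1/8 = 12.5% | 3/10 = 30% |

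If no withdrawn subject declined, the full-data figure is 10% and the plan is exact.

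**Expected size if the decrement risk among withdrawn subjects is p.** Expected bias = −(w/N) × p. With w = 2:

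- p = 10%: −0.2 × 10 = −2.0 points; chance that at least one decrement is hidden = 1 − 0.90² = 19%
- p = 20%: −4.0 points; 1 − 0.80² = 36%
- p = 34%: −6.8 points; 1 − 0.66² = 56%
- p = 50%: −10 points; 1 − 0.50² = 75%
- p = 100%: −20 points, the maximum

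The 34% is only an illustrative point in the range. Section 10.0 gives it as the rate of profound loss of functional acoustic hearing in the Hybrid L24 trial; it is not a CNC decrement rate.

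**Why the imputation should stay for the mean.** Assume nine completers each gain 20 points and one subject withdraws.

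| True change of the withdrawn subject | True mean | Imputed mean | Observed-only mean |
|---|---|---|---|
| −20 | (180 − 20)/10 = +16 | 180/10 = +18 | +20 |
| 0 | +18 | +18 | +20 |
| +20 | +20 | +18 | +20 |

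When the withdrawn subject has declined, the imputed mean overstates benefit by 2 points and the observed-only mean by 4. Dropping the imputation altogether would make that case worse.

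**The case against.** The strongest reply is that section 9.0 ties the imputation to the primary efficacy endpoint, which the synopsis describes only as a report of monosyllabic word performance at 12 months. No sentence says that imputed scores feed the three-way count in section 8.3. That is true, and the link is a reading of two sections together. It is the natural one: CNC is among the measures that section 8.3 covers, the three-way count is the only minimum efficacy summary defined there, and unchanged from baseline corresponds to its middle category. If the sponsor intends something else, the protocol needs a sentence to say so.

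Second, declines would not vanish. Individual data are tabulated, adverse events are reported separately, reasons for withdrawal are recorded, and section 7.1 denies primary-endpoint success to anyone who does not keep the original device. All this stands and limits the harm, but none of it corrects the decrement proportion itself.

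Third, the speech objectives ask about improvement, for which the rule is cautious, and a statistical analysis plan may add sensitivity analyses. The first part is right, and the imputation should remain for that purpose. Added sensitivity analyses would not change the direction of the primary rule that the protocol states.

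Fourth, the size is hypothetical, and the upper bound counts as worse even a subject whose last score had risen. This is fair. The bound is a limit and not an estimate, which is why the last observed score should stand beside it.

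**Conclusion.** The concern holds. On the natural reading of sections 8.3 and 9.0, the 12-month CNC decrement proportion can be biased downward and never upward. At N = 10 the understatement is 10 percentage points for each withdrawn subject who in truth declined: between 0 and 10 points with one withdrawal, and between 0 and 20 with two. It is zero if nobody withdraws or if no withdrawn subject declined.

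The direction is arithmetic. The size rests on assumed withdrawals and decrements, because the protocol gives neither. The point is confined to the 12-month CNC summary and leaves the improvement proportion, the individual listings and re-implanted subjects who remain in follow-up unaffected. It should be corrected, but it does not threaten the study.

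**What to change.** Amend section 9.0 so that, in the three-way CNC table:

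- withdrawn subjects stay in the denominator and count as not improved;
- they appear in their own row, labelled as having no 12-month result, with the last observed post-activation CNC score (3 or 6 months) in the same listening condition;
- the decrement proportion is given as a range, from none to all of these subjects counted as decrements.

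Keep baseline imputation for the improvement proportion and the mean change, and state that the pre-operative score used is from the listening condition matching the 12-month test. This needs saying because sections 5.4.1.3 and 5.4.2.1 produce several pre-operative CNC scores (each ear aided, and both ears aided). Do not substitute an observed-only mean.

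The cost is about one sentence in the protocol and one table row, using scores already scheduled. The small downside is that decrement is reported as a range and may look less favourable than a single figure.
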